5.1.3. Unblinding due to availability of other authorized/approved COVID-19 vaccines

In the double-blind phase of the study, investigators may receive requests to unblind study participants who become eligible to receive other COVID-19 vaccines if/when these are authorized/licensed for use. In these cases, the investigator will discuss with the participant available options and ramifications. If the participant is eligible for a licensed vaccine according to local immunization guidelines or recommendation and if the participant wishes to proceed with the unblinding, the investigator will follow the unblinding procedures. The reason for the unblinding request should be documented as ‘availability of other COVID-19 vaccine’. The date(s) of administration of the other COVID-19 vaccine should be recorded.

When unblinding, if it is determined that the participant received the Janssen vaccine (and not placebo), the participant will be informed that there are no data on the safety of receiving two different COVID-19 vaccines. Unblinded participants, both in the double-blind and open-label phase, will be asked to continue to be followed in this study in line with the schedule of activities to the extent that they permit. Safety evaluations will be identical for all participants, including participants that are unblinded to obtain another COVID-19 vaccine and who remain in the study, including participants in the safety subset, if applicable and feasible.

5.1.4. Unblinding due to cross-over for Janssen Vaccine

Section 6.4 from CTPA4 details the procedures to unblind participants at their Month6/Unblinding visit and offer participants who received placebo a single dose of Ad26.COV2.S vaccine. For all participants that are still in the study and did not have had a COVID-19 infection, nor have been censored, the Month6/Unblinding visit will mark the date of censoring for the double blind phase.

If participants decide to continue the study at the Month6/Unblinding visit, participants will be continued to be followed up and data will be collected and be analyzed separately.

5.1.5. Scope of Analysis of the double blind phase

The final analysis planned at the end of the double blind phase, comparing vaccine versus placebo, will include efficacy and safety data collected during the ‘double blind phase’ of the trial, i.e. with an onset date of the event (or censor date) up to unblinding.

To include the available data after unblinding, this analysis – comparing vaccine versus placebo – will be supplemented for primary and secondary endpoints with an analysis evaluating all available events up to the data lock point, until study discontinuation or upon administration of another authorized/approved vaccine up. The analysis will be censored at the date of another authorized/approved COVID-19 vaccine (if any, including the Janssen Vaccine if received outside of the study), the date of study discontinuation or the last available date (data lock point), whichever occurred first. Events that occurred after cross-over to another COVID-19 vaccine (including the Janssen Vaccine if received outside of the study) will be tabulated separately. Placebo recipients crossed-over to the Janssen COVID-19 vaccine (as part of the study) will be evaluated on placebo for the time they are exposed under placebo injection and evaluated for vaccine for the time they are exposed post Janssen COVID-19 vaccination.

The complete analysis of the open-label phase (comparing efficacy between immediate vaccination versus delayed vaccination with the Janssen COVID-19 vaccine during the open-label phase of the study will include efficacy and safety data after unblinding and will be described in a separate SAP. Per protocol amendment 5, this analysis is planned when all subjects had at least one year of follow-up.

5.2. COVID-19 case and SARS-Cov-2 infection classification

The initial COVID-19 classification will be based on a programmed algorithm (see section 5.2.2). Following the algorithmic assignment, all COVID-19 episodes and/or SARS-cov-2 infections (symptomatic and asymptomatic/undetected) will be assessed (case by case or with a sample approach as explained in the charter) independently by a Clinical Severity Adjudication Committee (CSAC, see Section 5.9.8). This committee will independently evaluate the severity of the COVID-19 cases in a blinded manner, confirm the onset date as proposed by the algorithm or adapt the onset date based on clinical judgement and whether a case required medical intervention through objective findings.

Classification in terms of severity will be based on the highest degree of severity during the observation period. The assessment per CSAC is considered the final classification.

The process of adjudication is described in a separate charter, the relevant details regarding case classification are inserted in section 5.2.2.

5.2.1. Identification of COVID-19 cases for adjudication

All COVID-19 episodes and/or SARS-cov-2 infections since the start of the study will be identified using a programmed algorithm described in the section 5.2.2. All fatalities that occur within the study for which COVID-19 could be a contributory or the underlying cause of death will be sent for adjudication, including fatalities not identified by the programmed algorithm. In

addition, cases may be flagged for adjudication through the use of other sources such as the Global Medical Safety database.

All cases identified by the algorithm as severe/critical (tier I)^a or mild (tier V)^a will be sent for adjudication for review on a case by cases basis.

Similarly, moderate cases identified by the algorithm will be sent for adjudication when they have at least one flag=Y for (tier II):

- SpO₂ ≤93% from any source
- Heart rate ≥125 beats/minute
- Respiratory Rate ≥30 breaths/minute
- Medical Attended/MA-COV

In addition, a moderate case identified by the algorithm that resulted in hospitalization will be sent for adjudication.

For all other cases identified by the algorithm as moderate (tier III if 3 or more signs/symptoms, tier IV if <3 signs/symptoms)^b, adjudication may be performed for only a proportion of such cases, i.e. a sample approach. That is, the CSAC will be presented with the programmed algorithm outcomes and be asked to review a sample of such cases. Based on the results of these “sample adjudications”, the CSAC will make a recommendation whether the programmed algorithm can serve as the default method of adjudication for the remainder of such cases.

Participants identified by the algorithm as asymptomatic/ undetected infections based on a PCR positive result during the course of their participation in the study and/or based on having seroconverted during their study time will be sent for adjudication only when the algorithm captures the presence of COVID-19 symptoms at any point up to 7 days prior to the onset of an algorithmic asymptomatic SARS-CoV-2 infection or prior to seroconversion.

Cases will be considered ready for adjudication at the time of case resolution and when the data have been cleaned. Case resolution is defined as two consecutive negative RT-PCRs and two consecutive days without symptoms. Alternatively, a case can be considered resolved when 30 days have elapsed since its onset. In either situation, a case is considered valid for adjudication when the critical factors related to the case definition have been cleaned. Cases that have not resolved and/or been cleaned may be adjudicated when necessary to comply with regulatory filing requirements (e.g., interim analysis or Biologics License Application (BLA)).

^a Tier definitions: Tier I: severe cases, Tier II moderate cases with at least one flag=Y (SpO₂ <=93%, heart rate >=125 beats/minute, respiratory rate >= 30 breaths/minute, medically attended/MA-COV), Tier 3: moderate cases with >=3 symptoms, Tier IV: moderate cases with <=2 symptoms, Tier V: mild cases.

^b Tier definitions: Tier I: severe cases, Tier II moderate cases with at least one flag=Y (SpO₂ <=93%, heart rate >=125 beats/minute, respiratory rate >= 30 breaths/minute, medically attended/MA-COV), Tier 3: moderate cases with >=3 symptoms, Tier IV: moderate cases with <=2 symptoms, Tier V: mild cases.

The final adjudication under the previous charter version was completed on 12th April 2021. As of that date, case identification and adjudication following the current charter version (19 May 2021) will become applicable. New cases identified following the processes described in this section will be adjudicated retrospectively from study start, following the same principles described above. In addition, the following subsets of cases may be re-adjudicated following the methods stipulated in the charter:

- Cases previously adjudicated as not severe/critical where the programmed algorithm now demonstrates a change in severity classification.
- Cases where a critical data point has changed due to subsequent data cleaning.
- Cases previously adjudicated that were subsequently hospitalized (without additional data that changed the tiered classification detailed above). These cases will not be re-adjudicated on the severity classification, rather, the CSAC will be asked to adjudicate the onset date and to judge whether hospitalization/emergency room care for the COVID-19 episode was linked to objective measures

5.2.2. COVID-19 case classification relevant definitions

Definitions relevant to COVID-19 case classification are listed below.

- **Episode** (of COVID-19): An episode of COVID-19 is defined as the period of the onset of (COVID-19) symptoms up until resolution of the episode. The severity of a COVID-19 will be determined based on the maximum severity observed across the episode.
- **Onset of (COVID-19) symptoms:** This is the date when any sign(s) or symptom(s) suggesting possible COVID-19. It will be called Day 1 of an episode. It is the earliest date the first symptom of an episode entered on the eCOA or on the CRF if entered by the site (“*If a participant records in the eCOA or informs the site that he/she experienced any signs or symptoms suggesting possible COVID-19, this will be considered COVID-19 Day 1 (day of onset of signs and symptoms).*” CTP) or the AE onset date if linked to COVID-19 (The following preferred terms are included in this analysis: "COVID-19", "ASYMPTOMATIC COVID-19", "SUSPECTED COVID-19", "COVID-19 PNEUMONIA" and "SARS-COV-2 TEST POSITIVE"). [Day 1 will be derived based on the first symptoms that are entered in the eCOA before the first swab is taken. In case there are multiple days with symptoms entered in the eCOA before the first swab, Day 1 is the earliest Day of all consecutive Days with signs or symptoms that are at least mild. Days without symptoms within 7 days before the first swab will be ignored in the evaluation of consecutive days.] A sensitivity analysis will be done to evaluate the change in onset date based on the 7 day window compared to the algorithm implemented at the primary analysis, where a day without symptoms interrupted the consecutive Days.
- **Resolution of an episode:** Resolution of the COVID-19 episode is defined as having 2 consecutive SARS-CoV-2 negative nasal swabs and 2 consecutive days with no COVID-

19-related signs or symptoms. [The date taken will be the first of the 2 consecutive negative swabs, OR the first day with no COVID-19 related signs or symptoms, whichever comes last. For this determination, all sources of information will be used (eCOA, eCRF or an AE linked to COVID-19). In case of missing days, it will depend if those are before or after the first day of the two consecutive SARS-CoV-2 negative nasal swabs. If before days with missing data have no consequence. If after, it is assumed that if days with missing data are after a day with no symptoms, the subsequent days also were without symptoms. If days with missing data are after a Day with symptoms, the assumption depends on the data of subsequent Days. If there are no more than 2 Days without data and the next Day does have (at least mild) symptoms, the missing days will be assumed to also have had symptoms. In all other cases it will be assumed that days with missing data were without symptoms and the rule to determine the resolution of symptoms will be applied.]

- **Molecularly confirmed case:** Events for which at least one SARS-CoV-2 PCR positive test was obtained by the University of Washington central testing facility.
- **A suspected COVID-19 case** is a case which meets any of the symptomatic COVID-19 definitions according to the CSAC without a document PCR positive results (any source) or a positive serology test.

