5.5.3. Supportive Secondary Endpoint(s)

To understand and characterize the vaccine efficacy against any symptomatic infection, as well as under any infection, the following supportive endpoints will be supplemented with the confirmatory secondary endpoints.

The evaluation of secondary endpoints will be done in the per-protocol analysis set in seronegative subjects, with onset at least 14 and at least 28 days after double-blind vaccination. All analyses will be repeated regardless of serostatus.

	Endpoint definition
Mild infection	A subject is considered as an event when the first occurrence of molecularly confirmed COVID-19 case meeting mild definition with onset at least 14 and at least 28 days post double-blind vaccination.
Moderate infection	A subject is considered as an event when the first occurrence of molecularly confirmed COVID-19 case meeting moderate definition with onset at least 14 and at least 28 days post double-blind vaccination.
US FDA Harmonized COVID-19 cases	A subject is considered as an event when the first occurrence of molecularly confirmed COVID-19 case meeting the US FDA harmonized case definition with onset at least 14 and at least 28 days post double-blind vaccination
Viral Load AUC (VL-AUC)	
Area under the viral load-time curve (VL-AUC in \log_{10} copies/ml) of SARS-CoV-2 viral RNA load as determined by quantitative RT-PCR assay of nasal available samples during the COVID-19 episode.
 
Nasal swab samples are taken at the start of the COVID-19 episode and every 2 days thereafter for the next 14 days or until 2 consecutive negative swabs, whichever occurs later.
 
VL-AUC is calculated based on the viral load values until resolution of the COVID-19 episode.
 
In the calculation of the AUC, all available information (date, timing in hours, and minutes as captured in the data base will be used, but the AUC result will be reported in hours), of the assessment, is taken into account.
 
Data handling regarding the following will be added to the Data Presentation Specifications (DPS):
 
 • PCR local lab versus central lab data • saliva • handling of values below LLOQ/LLOD

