To evaluate if the vaccine induces a reduction of severity, the patient-reported outcomes (PROs) in relation to the presence of SARS-CoV-2 infection across case definitions are investigated. The presence, severity and duration of COVID-19 signs and symptoms are captured in multiple scores and statistics as described in section 5.8.4 and are compared for subjects with a SARS-CoV-2 infection between the vaccine group and the placebo group. Mean differences of scores and statistics are tabulated as well as graphically presented. Additionally, examination of the severity of symptoms over time will be done graphically by presenting symptom scores over time and will be used to explore differences in severity profiles over time between vaccination groups. A Markov multistate chain analysis on the severity changes over time may be applied to compare between vaccinated and placebo group with an associated p-value and confidence intervals .

Furthermore an analysis of the composite scores of the PROs will be done to possibly depict stronger reduction of severity of certain specific domains of symptoms for vaccinated subjects versus placebo subjects.

Lingering of symptoms

Time to resolution of symptoms will be presented by a Kaplan-Meier curve for participants in the Ad26-CoV-2 and placebo groups and will be compared with a log rank test with associated p-value and confidence interval if applicable. This analysis will be supplemented by time to resolution of domain specific symptoms using the composite scores as described in section 5.8.4

Relation between viral load and symptom reduction and pattern

Furthermore the association between viral load and symptoms may be explored graphically as well as via longitudinal modeling, at an individual level and a population level

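### After the first of two negative swabs, a reporting gap of three or more days, or no further reports, is imputed symptom-free, so participants whose last or next recorded day is symptomatic are scored as resolved

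*SAP*

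**What the plan says.** SAP section 5.2.2 defines resolution by two conditions together: two consecutive negative nasal swabs and two consecutive days free of COVID-19 signs and symptoms. On timing it says "The date taken will be the first of the 2 consecutive negative swabs, OR the first day with no COVID-19 related signs or symptoms", taking the later of the two. Symptom information comes from the eCOA, the eCRF and adverse events linked to COVID-19, so a day is missing only when all three are silent.

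For missing days, "it will depend if those are before or after the first day of the two consecutive SARS-CoV-2 negative nasal swabs":

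- Before that swab: "If before days with missing data have no consequence".
- After it, following a symptom-free day: the missing days are taken as symptom-free.
- After it, following a symptomatic day: the missing days are taken as symptomatic only under this condition: "If there are no more than 2 Days without data and the next Day does have (at least mild) symptoms".
- Anything else: "In all other cases it will be assumed that days with missing data were without symptoms", and the resolution rule is then applied.

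The sensitivity analysis stated in the same section concerns the onset date. None is stated for the missing-day rule at resolution.

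Section 5.6.1.2 describes time to resolution of episodes by arm with Kaplan-Meier methods and, if applicable, a log-rank test. Section 5.8.4.1 defines several symptom scores (AUC, peak) over the COVID-19 episode.

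**The concern.** Two symptom-free days are enough for the symptom condition. Under the default, a gap of three or more days meets it by itself, even when the next recorded day shows symptoms. Three groups of swab-negative participants are then scored as resolved against the data, or without data:

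1. those with symptoms recorded on both sides of a gap of three or more days;
2. those whose last record is symptomatic and who report nothing afterwards;
3. those with one recorded symptom-free day, then one missing day, then symptoms again.

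In a time-to-event analysis, group 2 should ordinarily be censored. Counting them as events treats silence as recovery. In groups 1 and 3 the event date is contradicted by later records of the same participant.

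The rule also differs from the plan's handling of similar questions. At onset (section 5.2.2), even recorded symptom-free days within seven days before the first swab do not break the run of symptoms. For viral clearance (section 5.6.1.1), a negative sample counts only if no later sample is positive. When sources disagree (section 5.2.3), the symptom is taken as present.

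**Working it through.** The plan gives no figure for this rule, so there is nothing to reproduce. The check applies the rule to an assumed participant.

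**Inputs from SAP section 5.2.2**
- N = day of the first of two consecutive negative swabs.
- S = first of two consecutive symptom-free days, after imputation.
- Resolution day R = max(N, S).
- A gap of L days after a symptomatic day, later than N, is symptomatic only if L ≤ 2 and the next recorded day has symptoms. Otherwise it is symptom-free.

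**Assumed inputs (illustration only)**
- N = 10, with the second negative swab on Day 12.
- Symptoms on every recorded day from Day 1 through Day 20, none from Day 21.
- The gap starts on Day 13, and all sources are silent during it.

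**Results**

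| Case | Imputation | S | R = max(N, S) |
|---|---|---|---|
| No gap | none | 21 | max(10, 21) = 21 |
| Gap of 1 or 2 days | symptomatic | 21 | max(10, 21) = 21 |
| Gap of 3, 4, 5 or 6 days | symptom-free | 13 | max(10, 13) = 13 |
| Last record symptomatic on Day 12, nothing later | symptom-free | 13 | max(10, 13) = 13, an event |
| Day 13 recorded symptom-free, Day 14 missing, symptoms again from Day 15 | Day 14 symptom-free | 13 | max(10, 13) = 13 |
| Gap on Days 13-15, but N = 18 | gap has no consequence | 21 | max(18, 21) = 21 |

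Moving from a two-day to a three-day gap shifts resolution by 21 − 13 = 8 days, although symptoms are recorded from Day 16 through Day 20. The last row shows the limit: the rule does nothing to a gap that precedes the first negative swab.

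**Contrast.** If any gap bounded by symptomatic days is kept symptomatic, R = 21 for every gap length from 0 to 6 days. The participant who falls silent after Day 12 is then censored on Day 12 instead of being an event on Day 13.

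**Symptom scores.** Section 5.8.4.1 counts symptom duration from the first to the last symptomatic day, which here gives 20 − 1 + 1 = 20 days. If only days before the imputed resolution on Day 13 count, it gives 12 − 1 + 1 = 12 days. The plan does not say which applies. AUC and peak score are tied to the episode and would lose Days 16-20 under the second reading.

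**Viral load AUC.** Section 5.5.3 says "VL-AUC is calculated based on the viral load values until resolution of the COVID-19 episode". R can never precede N, and section 5.5.4.5 sets undetected values to 0. Ending on Day 13 or Day 21 therefore changes the AUC only if viral RNA becomes detectable again.

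**The case against.** The strongest reply is that the rule reaches few people and few outputs. Most of this stands.

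- **Swabs.** Nobody is resolved on a gap alone. A reader might infer that anyone still ill or no longer reporting is scored as recovered. The text does not support that, because two consecutive negative swabs are always required.
- **Sources.** These are not simply diary gaps. A record in the eCRF or a linked adverse event fills the day.
- **Severity.** Section 5.2.2 says "The severity of a COVID-19 will be determined based on the maximum severity observed across the episode", so an early end of the episode might seem to lower severity and reach the co-primary endpoints. However, the adjudication committee's assessment is final (section 5.2), endpoints are analysed on it unless stated otherwise (section 5.2.6), and it uses all available relevant information, with re-adjudication on new information (section 5.9.8).
- **Lingering symptoms.** Section 5.6.1.3 says "Time to resolution of symptoms will be presented by a Kaplan-Meier curve", but does not say that the episode-resolution rule defines that event.
- **Bias.** One might argue that sicker placebo participants leave more gaps, so that a vaccine effect on duration is understated. The SAP gives no rate of missing days and nothing on gaps by arm.
- **Remedy.** Requiring two recorded symptom-free days from everyone would leave unresolved those who recover and stop reporting. Bridging gaps of any length could join separate illnesses. Both objections are sound, and neither change is proposed here.

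None of this removes the core defect. In the time-to-resolution analysis, the rule assigns an event date that later records contradict, and it turns non-reporting while symptomatic into recovery.

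**Conclusion.** The concern holds in a limited form. For swab-negative participants, the missing-day rule can date resolution before recorded continuing symptoms and scores those who fall silent while symptomatic as resolved. In the assumed example the error is 8 days and depends on one additional missing day. That figure illustrates the mechanism and does not estimate an average effect.

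The output clearly affected is the exploratory Kaplan-Meier and log-rank analysis of time to episode resolution. The episode-based symptom scores may be affected, depending on whether symptoms after the imputed resolution count. The SAP does not show a material effect on viral load AUC, adjudicated severity or the co-primary endpoints. The direction and size of any bias between arms cannot be determined from it.

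**What to change.** In SAP section 5.2.2:

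1. Do not let imputed symptom-free days establish resolution when the next recorded day within the same episode has symptoms. State a limit for the same episode, for example the 30 days since onset that section 5.2.1 already uses for case resolution.
2. Apply the same condition when one recorded symptom-free day is followed by missing data.

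In section 5.6.1.2:

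3. Censor participants whose last record is symptomatic at the last day with data in the time-to-resolution analysis, at least as a prespecified sensitivity analysis, and report the result under the present rule alongside.

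The cost is a few sentences and a small change to the derivation code. The downside is somewhat more censored durations. Reporting the number of participants whose resolution date rests on imputed days, by arm, would show whether the rule matters in practice.
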